5.1 PROTOCOL DEVIATIONS

Protocol deviations will be defined in Protocol Deviation Requirement Specification, including the classification of significance vs. non-significance. The number and percentage of patients with significant protocol deviations will be summarized by treatment group for the Enrolled Population. A listing of all significant protocol deviations will be provided.

6.0 DEMOGRAPHICS AND OTHER BASELINE CHARACTERISTICS

Demographic parameters and other baseline characteristics (eg, age, race, ethnicity, sex, weight, height, body mass index) will be summarized for all patients combined using the Enrolled Population, mITT Population, placebo responders of mITT Population, and placebo non-responders of mITT Population. An analogous analysis will be performed for baseline efficacy assessments.

Medical and surgical history, psychiatric history, previous treatment with psychotropic medication, and nondrug psychiatric treatment will be summarized by treatment group for the Safety Population.

The *World Health Organization (WHO) Drug Dictionary Enhanced* will be used to classify prior and concomitant medications by therapeutic class. *Prior medication* is defined as any medication taken before the date of the first dose of DB IP during the placebo lead-in period. *Concomitant medication* is defined as any medication taken on or after the date of the first dose of DB IP which is during the placebo lead-in period. If a medication started prior to the first dose of DB IP and continued into the placebo lead-in period, then this medication will be included in the analysis of prior and concomitant medications separately.

The number and percentage of patients with prior and concomitant medication use will be summarized by treatment group and Anatomical Therapeutic Chemical code for the Safety Population.

Multiple medications used by a patient in the same category will be counted only once in the summary tables. Concomitant medications started after the last visit of the randomized treatment period will not be summarized but will be included in the data listings.

Prior ADT treatment in the current episode, as recorded on ATRQ, will be summarized by frequency counts and percentages for patients who took each ADT in adequate dose and duration, total number of ADT taken at adequate dose and duration (ie., 1, 2, 3, or >3), and percentage of improvement reported (ie., $<25\%$, 25% to 49% , 50% to 75% , or $>75\%$).

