### 9.7.4 Extent of Exposure and Treatment Compliance

#### 9.7.4.1 Extent of Exposure

**Patients in the Safety Population will be categorized by the number of IP doses received. The number and percentage of patients in each category will be summarized by treatment group.**

*Prior medication* is defined as any medication taken before the date of the first dose of randomized IP. *Concomitant medication* is defined as any medication taken on or after the date of the first dose of IP.

Both prior and concomitant medication use will be summarized by the number and proportion of patients in each treatment group receiving each medication within each therapeutic class for the Safety Population. Multiple medication use by a patient will only be counted once.

*IV administration notes including site reaction at placement of IV, reaction to adhesive, infusion interruption, failure of administration device, increase in suicidality based on clinical evaluation, and perceptual disturbance based on mental status assessment are collected. For each item, the number and percentage of patients who had a 'yes' response will be summarized by treatment group and visit for the Safety Population.* The number and percentage of patients taking each qualifying ADT will be summarized by treatment group for the **mitT** Population. Mean daily dose for each qualifying ADT will be summarized using descriptive statistics (number of patients, mean, standard deviation [SD], median, *Q1*, *Q3*, minimum, and maximum) by treatment group for the **mitT** Population.

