7.3 TREATMENT COMPLIANCE OF BACKGROUND ADT

Dosing compliance for the background ADT during a specified period is defined as the total daily dose received by a patient during that period divided by the total daily dose prescribed during the same period as recorded in the eCRF multiplied by 100 regardless if a patient discontinued from the study. Descriptive statistics for ADT compliance will be presented for each ADT and overall by the treatment group for the randomized treatment period for the mITTPopulation.

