9.1 ADVERSE EVENTS

AEs will be coded using the *Medical Dictionary for Regulatory Activities* and reported separated for placebo lead-in, randomized treatment, and safety follow-up periods.

[figure not shown]
An AE (classified by preferred term) will be considered a treatment-emergent adverse event (TEAE) if it was not present before the first dose of DB IP (i.e. the first IP during the placebo lead-in period) or was present before the date of the first dose of DB IP and increased in severity after the first dose of DB IP. An AE that becomes serious after the date of the first dose of DB IP will also be considered as TEAE. If more than 1 AE was reported before the first dose of DB IP and coded to the same preferred term, the AE with the greatest severity will be used for comparison with the AEs occurring during each study period analyzed. An AE that occurred more than 30 days after the date of the last dose of DB IP (including the randomized IP) will not be considered as a TEAE.

[figure not shown]
The number and percentage of patients reporting TEAEs and TEAEs leading to study discontinuation in each treatment group will be tabulated by system organ class and preferred term and further categorized by severity and causal relationship to the IP. If more than 1 AE is coded to the same preferred term for the same patient, the patient will be counted only once for that preferred term using the greatest severity and strictest causality for the summarization by severity and causal relationship.

[figure not shown]
The incidence of common ($\geq 2\%$ of patients in any treatment group) TEAEs will be summarized by preferred term and treatment group and sorted by decreasing frequency for the test treatment.

[figure not shown]
A serious adverse event (SAE) that occurred between the date of the first dose of DB IP and 30 days after the date of the last dose of DB IP, inclusive, will be considered a treatment-emergent SAE (TESAE). The number and percentage of patients who have TESAEs will be summarized by preferred term and treatment group.

[figure not shown]
Listings will be presented for patients with SAEs, patients with AEs leading to discontinuation, and patients who die (if any). All patients with SAEs, including SAEs reported during the screening period and the safety follow-up period, and patients discontinuing because of AEs occurring before the start of randomized IP will be included in these listings.

[figure not shown]

[figure not shown]

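### The by-arm concomitant-medication table starts at the lead-in placebo dose, so it includes drugs taken and stopped before randomization (minor)

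*SAP*

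**What the plan says.** SAP 2.0 describes a one-week double-blind placebo lead-in, then 1:1 randomization, then two weeks of randomized treatment. The two periods together are called the double-blind treatment period.

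SAP 6.0 sets these rules for medication:

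- **Prior:** "any medication taken before the date of the first dose of DB IP during the placebo lead-in period".
- **Concomitant:** "any medication taken on or after the date of the first dose of DB IP which is during the placebo lead-in period".
- **Layout:** use "will be summarized by treatment group and Anatomical Therapeutic Chemical code for the Safety Population". No split by period is stated.
- **Counting:** "Multiple medications used by a patient in the same category will be counted only once in the summary tables".
- **End of window:** "Concomitant medications started after the last visit of the randomized treatment period will not be summarized".

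Elsewhere the SAP does separate the periods. In 9.1, adverse events are "reported separated for placebo lead-in, randomized treatment, and safety follow-up periods". In 7.3, compliance with background antidepressant is presented "overall by the treatment group for the randomized treatment period". In 14.7, incomplete medication dates are imputed around the first and last randomized doses.

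**The concern.** A by-arm medication table is normally read as showing whether the groups used other drugs to a similar extent while they were being compared. This table's window ends with randomized treatment but begins a week before assignment, so one of its three weeks belongs to neither arm. Everyone in the Safety Population was randomized, so each patient brings that week into an arm column. A drug taken only on Day 3 is reported under an arm to which the patient had not yet been assigned. Because the count is ever/never, the table cannot separate lead-in-only use from use under randomized treatment.

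At stake is how a descriptive comparison is read. No test or estimate depends on it.

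**Working it through.** The plan gives no figure on this point, so there is nothing to reproduce. The check has two parts: what the counting rule does, and how large the effect might be. **All usage rates below are assumptions.** The only figure taken from the documents is 210 patients per arm (SAP 12.0).

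**Step 1: which patients are counted.** For one drug class and one randomized patient there are four cases.

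| Lead-in | Randomized period | Counted under the arm by SAP 6.0 | Used during randomized treatment |
|---|---|---|---|
| no | no | no | no |
| no | yes | yes | yes |
| yes | yes | yes | yes |
| yes | no | **yes** | **no** |

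Only the last row is misplaced. Drugs continued past randomization belong in the table and cause no distortion.

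**Step 2: equal lead-in-only use.** Let *p* be the share of an arm using the class in the randomized period. Let *q* be the share of its remaining patients who used the class only in the lead-in. The table then shows

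p + (1 − p)q.

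If *q* is the same in both arms, the arm difference is multiplied by (1 − q) and the ratio moves toward 1. With true use of 10% versus 5% (difference 5.0 points, ratio 2.00):

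| q (assumed) | Table shows | Difference | Ratio |
|---|---|---|---|
| 2% | 11.8% vs 6.9% | 4.9 points | 1.71 |
| 5% | 14.5% vs 9.75% | 4.75 points | 1.49 |
| 10% | 19.0% vs 14.5% | 4.5 points | 1.31 |
| 20% | 28.0% vs 24.0% | 4.0 points | 1.17 |

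For q = 5%: 0.10 + 0.90 × 0.05 = 0.145, and 0.05 + 0.95 × 0.05 = 0.0975. With 210 per arm this adds 0.045 × 210 ≈ 9.5 and 0.0475 × 210 ≈ 10 patients who did not use the class after randomization. The absolute difference shrinks by 2% to 20% over this range. The ratio moves much more.

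**Step 3: stopping differs by arm.** Randomization makes total lead-in use equal in expectation, but not lead-in-only use, because treatment may affect who stops. Let *L* be the share using the class in the lead-in, *s* the share of the others who start it after randomization, and *c* the share of lead-in users who continue.

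- True randomized-period use: (1 − L)s + Lc
- SAP table: L + (1 − L)s

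The table does not depend on *c*, so an arm difference in stopping cannot appear in it. With *c* of 50% on rapastinel and 80% on placebo:

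| L | s, rapastinel vs placebo | True use | Table shows |
|---|---|---|---|
| 10% | 5% vs 5% | 9.5% vs 12.5% | 14.5% vs 14.5% |
| 10% | 10% vs 5% | 14.0% vs 12.5% | 19.0% vs 14.5% |
| 20% | 10% vs 5% | 18.0% vs 20.0% | 28.0% vs 24.0% |

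The first row removes a difference, the second overstates one, and the third reverses one. Dilution is the usual direction but not a certain one.

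**The case against.** **The anchor is a coherent convention.** SAP 9.1 defines treatment-emergent events from the first double-blind dose, and SAP 14.1 does the same for the safety baseline. A Safety Population medication table on the same anchor fits with these. That explains the choice of definition. It does not explain the missing split: SAP 9.1 uses the same anchor and still reports adverse events by period.

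**The consequences are small.** The table carries no test and feeds no efficacy model. Listings exist, and table specifications are in a separate document, where a split may appear. This stands and sets the severity. A listing is not a by-arm summary, however, and the SAP text does not call for a split.

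**The sizes are assumed.** This also stands. At low lead-in-only use the absolute difference barely changes. The permitted-drug rules for anxiety or agitation (protocol 9.4.10) are redacted, so it cannot be checked which relevant drugs were allowed. Protocol 9.4.1 holds background antidepressant dose constant, and 9.4.13 removes patients who start new treatment for worsening depression. Both limit the imbalance of most interest.

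**A reader might infer an undeclared departure from the protocol.** Protocol 9.7.4.1 says prior medication "is defined as any medication taken before the date of the first dose of randomized IP", the SAP uses the lead-in dose, and SAP 15.0 lists no such change. The documents do not support this inference. The same protocol section starts concomitant medication at the first dose of IP, without the word randomized, and the SAP agrees with that. The public protocol describes no lead-in: patients are randomized at Visit 2 and dosed that day (9.4 and 9.4.7.2), so its first randomized dose is the Visit 2 dose. The SAP also implements a Restricted Access Addendum that is not available here. An omission from SAP 15.0 cannot be shown, and there is no case for changing protocol 9.7.4.1.

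**Conclusion.** The point holds as a minor one. By the SAP's own rules, the by-arm concomitant-medication table includes drugs taken and stopped before assignment, so it does not show use during randomized treatment. This follows from the text and rests on no assumed rate.

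The size is unknown. If lead-in-only use is equal across arms, the absolute difference shrinks by that share and the ratio moves toward 1. If stopping differs by arm, the table can understate, overstate or reverse the difference.

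A reader might go further and infer that the table would hide an imbalance explaining the Day 21 result. The documents do not support that. They give no usage rates, they do not assign the table that role, and no efficacy analysis in SAP 8.1 or 8.2 uses it. The primary test is unaffected.

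**What to change.** Change SAP 6.0 only, and replace the single concomitant table with two:

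1. **Lead-in:** medication taken from the first double-blind dose to before the first randomized dose, for all patients combined.
2. **Randomized period:** medication taken on or after the first randomized dose, including drugs continued from the lead-in, to the last randomized-period visit, by treatment group. Use this table for the between-arm comparison.

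The cost is one extra table from dates already collected. Medications with incomplete dates must be assigned to a period. SAP 14.7 already anchors that imputation to the randomized doses. One limitation should be footnoted: a start date missing only its day, in the month of the first randomized dose, is set to that dose. Some lead-in-only drugs will therefore fall into the second table, unless a complete stop date moves the start back.

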7.0 EXTENT OF EXPOSURE AND TREATMENT COMPLIANCE

7.1 EXTENT OF EXPOSURE OF STUDY TREATMENT

The number and percentage of patients who received 1 or 2 randomized IV doses will be summarized by treatment group for the Safety Population. IV administration notes including site reaction at placement of IV, reaction to adhesive, infusion interruption, failure of administration device, increase in suicidality based on clinical evaluation, and perceptual disturbance based on mental status assessment are collected. For each item, the number and percentage of patients who had a 'yes' response will be summarized by treatment group and visit for the Safety Population.

7.2 EXTENT OF EXPOSURE OF BACKGROUND ADT

The number and percentage of patients taking each qualifying ADT will be summarized by treatment group for the mITT Population. The mean daily dose for a patient over a study period is defined as the total daily dose administered by a patient during that study period as captured on the CRF, divided by the duration the patient participants in that study period, measured in days. The mean daily dose for each ADT will be summarized using descriptive statistics (number of patients, mean, SD, median, minimum, and maximum) by treatment group for the mITT Population.

7.3 TREATMENT COMPLIANCE OF BACKGROUND ADT

Dosing compliance for the background ADT during a specified period is defined as the total daily dose received by a patient during that period divided by the total daily dose prescribed during the same period as recorded in the eCRF multiplied by 100 regardless if a patient discontinued from the study. Descriptive statistics for ADT compliance will be presented for each ADT and overall by the treatment group for the randomized treatment period for the mITTPopulation.

7.4 WEIGHT ADJUSTED DOSE OF RAPASTINEL

The dose of rapastinel will be divided by patient baseline weight and summarized by descriptive statistics including total number of patients who received rapastinel, mean, standard deviation, minimum and maximum for the Safety Population.

8.0 EFFICACY ANALYSES

All efficacy analyses will be based on the mITT Population, unless stated otherwise. The baseline for each specific efficacy endpoint is defined as the last measurement prior to the first dose of randomized treatment. The Day 0 measure for each specific efficacy endpoint is defined as the last measurement prior to the first dose of double-blind IP in the placebo lead-in period. The analyses for the placebo lead-in period will be presented for all patients combined and separately for the placebo responders vs. non-responders using the Enrolled Population. All statistical hypothesis tests will be performed at the 2-sided 5% significance level for main effects. All confidence intervals (CIs) will be 2-sided 95% CIs, unless stated otherwise.

For efficacy analyses in which study center is a factor, a *small center* will be defined as a center with less than 2 placebo non-responder patients in at least 1 treatment group in the mITT Population. Small centers will be pooled to form pseudo-centers so that each treatment group includes at least 2 placebo non-responder patients within the center for the mITT population. Pooling will be done using the following algorithm:

Based on the number of placebo non-responder mITT patients, small centers will be ordered from the largest to the smallest, and centers of the same size will be ordered from the largest center number to the smallest center number. The pooling process starts with the largest small center from the top, which will be pooled with the smallest from the bottom until a non-small center is formed. The process will be repeated using the small centers left out after the first pass. If any centers are left out at the end of the process, they will be pooled with the smallest pseudo-center. If there is more than 1 smallest pseudo-center, the pseudo-center with the smallest center number will be selected. In case the pseudo-center formed by pooling all small centers is still a small center, it will be pooled with the smallest non-small center. If there is more than 1 smallest non-small center, the one with the smallest center number will be selected.

If any, the centers with only placebo responder patients will be ordered from largest to the smallest by the number of patients. The smallest pooled center (based on placebo non-responder as defined in the previous paragraph) will be combined with largest center with only placebo responder patients; the second smallest pooled center (based on placebo non-responder as defined in the previous paragraph) will be combined with the second largest center with only placebo responder patients; the remaining centers with only placebo responder patients will be combined similarly. Centers with same number of patients will be further ordered by the center code.

The final pooled pseudo-centers will be used for all efficacy analyses when the model is adjusted for study center.

The efficacy analyses of MADRS assessments will be based on the rater-administered MADRS. The efficacy analyses using the mITT population will be performed based on the treatment to which the patient is randomized regardless of the actual treatment received. If a patient is randomized based on an incorrect stratum, then this patient will be analyzed according to the stratum to which the patient should have been assigned per the electronic data capture system, instead of the stratum per the randomization system of IWRS.

8.1 PRIMARY EFFICACY PARAMETER

The primary efficacy parameter will be the change from baseline to Day 21 in MADRS total score for the mITT population. The MADRS total score is the sum of the 10 individual items. If more than 2 items are missing, then the total score will be set to missing. If there are multiple assessments of MADRS total score for the same nominal visit of a patient, only the last assessment will be used in the analysis.

The primary efficacy parameter will be analyzed using a mixed model for repeated measures (MMRM) with treatment group, pooled study center, visit, placebo responder status at Day 7, and treatment group-by-visit interaction as the fixed effects, and Day 0 MADRS total score, baseline MADRS total score, Day 0 MADRS total score-by-visit and baseline MADRS total score-by-visit interactions as covariates. An unstructured covariance matrix is used to model the covariance of change in scores within patients. The Kenward-Roger approximation will be used to estimate denominator degrees of freedom ([Kenward et al, 1997](#)). The analysis will be performed based on all post-randomization data using only the observed cases without imputation of missing values.

In the case that the MMRM model with unstructured covariance fails to converge with the default algorithm, then the Fisher scoring algorithm will be used to provide better initial values of the covariance parameters; if the model still does not converge, a simplified model without term for study center will be used to find the initial values of the covariance parameters. In the rare event that the model still does not converge after using those initial values, simplified covariance structures will be used to fit the model in the following order until the model converges: (1) ante-dependence, (2) heterogeneous autoregressive, (3) Toeplitz, and (4) compound symmetry.

To assess the robustness of the primary MMRM results to the possible violation of the missing-at-random assumption, a sensitivity analysis using a pattern-mixture model based on non-future dependent missing value restrictions (Kenward et al, 2003) will be performed. The pattern for the pattern-mixture model will be defined by the patient's last visit with observed value. The observed MADRS total score at a visit is assumed to have a linear relationship with the patient's prior measurements. The missing values will be imputed under the assumption that the distribution of the missing observations differs from the observed only by a shift parameter value Δ . The dataset with missing values will be analyzed using the same model as the primary analysis for between-treatment group comparisons. The imputation of missing values and the analysis will be performed multiple times and the inference of this sensitivity analysis will be based on the combined estimates using the standard multiple imputation technique. The values for Δ will be selected as 0 to 8.

[figure not shown]
